5.2.1 Autoimmune disorders

For this category, the primary events are Systemic Lupus Erythematosus and Rheumatoid Arthritis.

The diagnosis has to be supported with medical history and physical findings, serologic evidence and other evidence from biopsy, laboratory results, imaging results, or other specialized testing, where appropriate, and the exclusion of other disorders which might cause a similar pattern of findings.

5.2.2 Demyelinating disorders

For this category, the primary event is Multiple Sclerosis. Guillain-Barre syndrome and chronic inflammatory demyelinating polyneuropathy will be analyzed as autoimmune disorders.

Medical history and physical findings, laboratory results, imaging results (eg, MRI) and any other specialized test (EEG, EMG, CSF analysis) results have to be considered in determining the final diagnosis.

5.2.3 Serious and Opportunistic Infections

Serious infections are defined as all infections meeting the definition of an SAE, and/or an infection requiring parenteral administration of antibiotics.

For the opportunistic infection category, the primary events are tuberculosis and pneumonia. The definitive diagnosis of pneumonia and tuberculosis may be confirmed by obtaining sputum smears or relevant biopsies and verifying by cultures. Infections not usually seen in immunocompetent patients or infections that have an accelerated pathogenesis or a more severe outcome in a given setting will also be considered opportunistic infections.

5.2.4 Lymphoma and Other Malignancies

For this category, the primary events are lymphoma, including hepatosplenic T cell lymphoma and non-Hodgkin lymphoma, and solid malignant tumors which are captured on malignancy forms.

Diagnosis has to be confirmed by tissue biopsy for histopathology (sources of tissue samples for review may include those obtained from an excisional biopsy) -a tissue sample from the affected nodes or organ, a needle aspiration, or a bone marrow biopsy. Pathohistological results have to correlate clinically with imaging results and/or any other pertinent information prior to determining the final diagnosis.

5.2.5 Hypersensitivity Reaction

Primary endpoints for hypersensitivity reaction are events meeting the criteria of an anaphylactic reaction and acute hypersensitivity reaction occurring within 2 hours of drug administration. As described in the case definition below, anaphylactic events include all terms listed in Category A, which consists of the narrow terms Type I hypersensitivity, anaphylactic shock and anaphylactoid reaction. In addition, combinations of the AE terms listed in Categories B, C and D will also be defined as anaphylactic events.

Category A: anaphylactic reaction, Type I hypersensitivity, anaphylactic shock, anaphylactoid reaction

Category B: dyspnoea, chest discomfort, cough, swollen tongue, oedema mouth, throat tightness, wheezing, laryngeal oedema, respiratory distress, sensation of foreign body, asthma, sneezing

Category C: swelling face, urticaria, pruritus, rash, eye swelling, pruritus generalized, rash, generalized, flushing, erythema, swelling, eye pruritus, lip swelling, rash pruritic, rash, erythematous, eyelid oedema, ocular hyperaemia, injection site urticaria, angioedema

Category D: hypotension, blood pressure decreased

To meet the definition of an anaphylactic event, a case has to meet one of the following criteria:

1. A narrow term or a term from Category A;
2. A term from Category B (Upper Airway/Respiratory) AND a term from Category C (Angioedema/Urticaria/Pruritus/Flush);
3. A term from Category D (Cardiovascular/Hypotension) AND either a term from Category B (Upper Airway/Respiratory) or a term from Category C (Angioedema/Urticaria/Pruritus/Flush)

5.2.6 Congestive heart failure

Congestive heart failure (CHF) is the primary endpoint for cardiac events of interest. CHF will be defined by Framingham criteria. The diagnostic criteria include physical findings of low cardiac output or increased cardiac workload and radiographic evidence (chest X-ray,

ECG, Echocardiogram, CT, MRI, angiogram) and laboratory findings, ECG and imaging results and any other specialized test results have to be considered for final diagnosis. CHF present at baseline and worsening during the study (worsening of New York Heart Association (NYHA) functional classification) will be captured, as well as new onset CHF.

5.2.7 Aplastic anemia

Aplastic anemia is a primary endpoint. Diagnosis must be confirmed by complete blood count (CBC) with peripheral smear, and bone marrow biopsy. Findings of pancytopenia (neutropenia, thrombocytopenia, and anemia), a reduction in the absolute number of reticulocytes, and a hypocellular bone marrow could be used to confirm the diagnosis.

5.2.8 Serious bleeding events

For this category, bleeding events meeting the criteria of an SAE are primary endpoints.

5.2.9 Serious skin reactions

For this category, primary endpoints are Erythema multiforme, Stevens Johnson's syndrome, and Toxic epidermal necrolysis.

5.3 Anticipated Serious Adverse Events

The following list of Anticipated SAEs has been identified as these events are anticipated to occur in the population studied in this protocol at some frequency that is independent of drug exposure. This original list will remain in effect for the duration of the protocol.

This list does not change the Investigator's obligation to report all serious AEs (including Anticipated SAEs) as detailed in Section [5.4](#).

Crohn's disease
perianal abscess
abdominal pain

5.4 Adverse Event Reporting to the Registry

Serious adverse events and AEs of interest are the focus of this registry; Investigators are expected to enter all SAEs and AEs of interest in the eCRF.

All SAEs and all AEs of interest will be entered in the EDC system within 24 hours of site notification and will be automatically forwarded to PRA, International for assessment and further processing as per regulatory requirements and UCB procedures (see [Figure 5-1](#), Event Reporting Process for flow of activity).

Any major changes in health status reported by the patient during the every 3 month patient follow-up will be sent to the Investigator for medical confirmation. Once medical confirmation is obtained, the Investigator will report the event through the EDC system.

To ensure the capture of any events that might occur between patient or Investigator data entry intervals, each patient will be provided a safety reporting process patient card that they

can present to an Investigator if they have an event. The card will contain instructions for the Investigator on how to report event information.

Information and instructions informing patients about the Follow-Up Period and how to report AEs is included in the Informed Consent Form. More detailed instructions to sites regarding reporting of SAEs and AEs of interest are provided in the UCB safety Guidance booklet.

[figure not shown]
5.5 Pregnancy and Breastfeeding

Investigators are required to report pregnancy and breastfeeding of study participants; and pregnancy of study participant partners. An informed consent form will be provided to a study participant's partner who becomes pregnant during the study; and who will be willing to provide information on pregnancy course and outcome. More detailed instructions to sites regarding reporting of pregnancy and breastfeeding are provided in the UCB safety Guidance booklet.

5.6 UCB Pharmacovigilance Reporting

Adverse events collected from the registry that occur within 70 days of last Cimzia dose will be included in UCB's safety database and reported to the FDA as per regulatory reporting guidelines. Registry cases of malignancy, death, and pregnancy will be included in UCB's safety database and reviewed and evaluated for FDA reporting even if the event occurs after 70 days of last Cimzia dose. Any reports received prior to start of the registry and after completion of the study will be evaluated and reported as per standard UCB pharmacovigilance plans for spontaneous reporting.

Figure 5–1: Event reporting process

AE=adverse event; EDC=electronic data capture; SAE=serious adverse event

6 STATISTICAL CONSIDERATIONS

6.1 Endpoints

The objective of this registry is to measure the safety outcomes among Cimzia patients compared to those that occur while on a different CD treatment.

6.1.1 Primary Endpoints

The primary outcome of this observational study is malignancy. Additionally, the following safety events will be investigated:

- Autoimmune disorders
- Demyelinating disorders
- Serious infections or opportunistic infections
- Hypersensitivity reactions
- Other events:
 - congestive heart failure
 - aplastic anemia
 - serious bleeding events
 - serious skin reactions

MedDRA coding version 17.0 will be used to identify and define AEs of interest. The specific MedDRA codes used to determine AEs of interest will be provided in the SAP. Narrow scope SMQs and clinical validation of primary endpoints are provided in Section [5.2](#) of the protocol.

6.1.2 Secondary Endpoints

Secondary endpoints include the following:

- Changes in HBI rating scale from baseline to each post-baseline assessment
- Changes in Investigator's assessment of disease from baseline to each post-Baseline assessment
- Changes in the patient's disease assessment of disease from Baseline to each post-Baseline assessment

6.2 Comparator Group

Given that patients will be followed for 8 years, it is anticipated that patients will switch CD medications while enrolled in the registry. Therefore, an individual's treatment at baseline will most likely not reflect their exposure throughout the study. Two comparisons may be

used to reflect these treatment changes over time and provide context for events reported to the registry: (1) a comparison of Cimzia event rates compared to all other CD treatment event rates across patients, and (2) case-crossover comparison or a within patient comparison.

- Cimzia event rates versus all other CD treatment event rates

Incidence and recurrence rates may be calculated for Cimzia and compared to all other CD treatment event rates across patients. Class-specific and product-specific event rates may also be calculated, if appropriate.

- Case-crossover comparisons

Case-crossover studies are useful for investigating the effect of transitory exposures on acute events. By having patients act as their own controls, this design eliminates between-person confounding on non-time varying characteristics, such as baseline disease and treatment characteristics and gender. However, there is still the potential for within-person confounding due to changes in the patient's profile over time (eg, changes in prescribing or in disease severity).

The incidence of safety events with short-term latency may also be compared within patients for patients that switch treatments at the time of enrollment into the registry and/or while participating in the registry. For this type of comparison, if applicable, the incidence of events of short-term latency within the first 6 months of receiving a new treatment may be compared to the incidence of the same events when beginning another new treatment.

6.3 Determination of Sample Size

Prior to Amendment 5, the study planned for a total of 4000 patients (2000 patients per arm). A total of 3045 patients (1371 in the Cimzia Cohort and 1674 in the Comparison Cohort) were enrolled as of Mar 2017. The total duration of participation (treatment and follow-up) of 8 years is planned for each patient. Assuming an 8% annual drop-out rate (1) (withdrawal, lost-to-follow-up or death), approximately 25,000 (12,500 per arm) total patient years (p-y) post-enrollment is expected in this registry. With a two-sided significance level of 0.05, the study is designed to have at least 80% power to detect incidence rate ratios (calculated based on observed rates in the control group) of 1.5 for serious infections, 3.3 for lymphoma, and 1.56 for solid malignancies after 8 years. Event rate estimates for this study were calculated using corresponding event rates observed in a CD anti-TNF α registry study control group (1, 2).

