2.3 Study design and conduct

Following protocol amendment 5, this long-term observational study in the USA stopped enrollment with approximately 3045 patients enrolled since study start. From the original study design, approximately half of enrolled patients will be receiving Cimzia for ≤ 12 months or about to receive Cimzia at the time of enrollment. The study will be conducted in all regions in the USA at approximately 280 enrolling investigative sites (community based and academic practice).

Recruitment of Cimzia-treated and comparator patients will be monitored and controlled as needed, and to ensure balanced enrollment over time between both cohorts, recruitment will be matched for disease severity (mild/moderate/severe), age categories and gender.

Patients will be followed for approximately 8 years (reduced from 10 years in protocol amendment 5) during normal physician visits and through direct patient follow-up in the form of web, mail surveys and/or phone follow-up calls. All patients will receive and use their medications according to their normal course of medical treatment per physician clinical judgment.

Follow-up data on the patients will be reported by physicians approximately every six months following enrollment while direct patient follow-up data will be collected quarterly via internet, mail or telephone.

Quarterly progress reports will be generated and sent to the FDA during the patient enrollment period. Subsequently, more detailed yearly informal interim analyses may be conducted to provide updates for regularly scheduled steering committee meetings or to the FDA on the information collected in this study. As agreed with FDA, the study is ending on 28 August 2020, and a single final study report will be submitted in 2021.

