2.4 Determination of sample size

Assuming an 8% annual drop-out rate (1) (withdrawal, lost-to-follow-up or death), approximately 25,000 (12,500 per arm) total patient years (p-y) post-enrollment is expected in this registry. With a two-sided significance level of 0.05, the study is designed to have at least 80% power to detect incidence rate ratios (calculated based on observed rates in the control group) of 1.5 for serious infections, 3.3 for lymphoma, and 1.56 for solid malignancies after 10 years. Event rate estimates for this study were calculated using corresponding event rates observed in a CD anti-TNF α registry study control group (1, 2).

Prior to Amendment 5, the study planned for a total of 4000 patients (2000 patients per arm). A total of 3045 patients (1371 in the Cimzia Cohort and 1674 in the Comparison Cohort) were enrolled as of Mar 2017. The total duration of participation (treatment and follow-up) of 8 years is planned for each patient. At the time of the final analysis, 3076 patients were enrolled in the study.

Prior to Amendment 5, the study planned for a total of 4000 patients (2000 patients per arm). A total of 3045 patients (1371 in the Cimzia Cohort and 1674 in the Comparison Cohort) were enrolled as of Mar 2017. The total duration of participation (treatment and follow-up) of 8 years is planned for each patient. At the time of the final analysis, 3076 patients were enrolled in the study.

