3.2.1.1 Person-time at risk calculations for malignancy

Due to the long latency of malignancy, gaps in exposure between treatments will be attributed to the most recent, previous treatment. Gaps in exposure before first known treatment will not be factored into person-time calculations for these events. Any patient exposed to Cimzia during the study will only contribute person-time to the Cimzia cohort from that point onward (Figure 1). As an example, if a malignancy should occur any time after Cimzia exposure (including when Cimzia was known to be used prior to enrollment), it will be attributed to Cimzia. If a malignancy occurred in a patient prior to Cimzia exposure or in a patient with no Cimzia exposure, then it would be attributed to comparator. Thus, a patient may have exposure to multiple comparator drugs, but any malignancies diagnosed after treatment with Cimzia would be systematically attributed to Cimzia, even after ending or switching from Cimzia.

Figure 1: Example person-time at risk for malignancy events

Exposure person-time at risk will be calculated for each CD treatment using the following equation:

$$\text{Last Date} - \text{First Date} + 1$$

where all person-time is contributed to Cimzia after first Cimzia dose is administered.

First date is defined as the latest enrollment date or first CD treatment date after enrollment (whichever is later) or first Cimzia dose date if switching from a comparator treatment after enrollment. Last date is defined as the earliest of the following:

- Date of safety event of interest (for incidence rate calculations only)

- Date of discontinuation, withdrawal, or data cutoff

See Section 11.1, appendix 1 for more examples of treatment allocation scenarios for malignancies.

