5 STUDY POPULATION CHARACTERISTICS

5.1 Subject disposition

The number and percentage of patients who enrolled and the number and percentage of patients who completed the study will be presented, together with the number and percentage of patients who withdrew from the study prematurely and a breakdown of the corresponding reasons for discontinuation will be produced by enrollment cohort and actual treatment at Baseline.

A Cox proportional hazards model utilizing Kaplan-Meier methods for time to discontinuation by year 1, year 2, ..., year 8, will be performed by enrollment cohort and actual treatment at Baseline. Discontinuation status, discontinuation time (median, 25th and 75th quartiles and corresponding two-sided 95% confidence intervals), and a hazard ratio and exploratory p-value from a log-rank test at $\alpha=0.05$ overall significance level will be included for the analysis of each year.

A Cox proportional hazards model utilizing Kaplan-Meier methods for time to discontinuation by year 1, year 2, ..., year 8, will be performed by enrollment cohort and actual treatment at Baseline. Discontinuation status, discontinuation time (median, 25th and 75th quartiles and corresponding two-sided 95% confidence intervals), and a hazard ratio and exploratory p-value from a log-rank test at $\alpha=0.05$ overall significance level will be included for the analysis of each year.

A summary of expected and actual patient retention by enrollment cohort and actual treatment at Baseline will include total patient-years and the number of patients followed for at least 1 year, at least 2 years, ..., at least 8 years.

Time to discontinuation will be analyzed using two different censoring rules (A and B).

According to censoring rule A, the time for patients in the Cimzia cohort will be censored when they switch to Comparator treatment and the time for patients in the Comparator cohort will be censored when they switch to Cimzia treatment. According to censoring rules B, time for all patients will be censored when they switch from one biologic treatment to another biologic treatment.

A table summarizing the number and percentage of patients enrolled at each site by enrollment cohort will be presented.

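### The expected 25,000 patient-years cannot come from 3045 patients followed for 8 years with 8% annual drop-out (about 17,800), so the stated 80% power is unsupported

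*Protocol*

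**What the plan says.** Protocol 6.3 reports that "A total of 3045 patients (1371 in the Cimzia Cohort and 1674 in the Comparison Cohort) were enrolled as of Mar 2017", plans 8 years of participation for each patient and assumes 8% annual drop-out from withdrawal, loss to follow-up or death. In the same paragraph it says "approximately 25,000 (12,500 per arm) total patient years (p-y) post-enrollment is expected in this registry". It then claims at least 80% power, at a two-sided 0.05 level, for rate ratios of "1.5 for serious infections, 3.3 for lymphoma, and 1.56 for solid malignancies after 8 years". The control rates are attributed to another registry's control group, but their values are not given.

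SAP 2.4 repeats the 25,000 patient-years and the 80% power, but for "1.5 for serious infections, 3.3 for lymphoma, and 1.56 for solid malignancies after 10 years". The same section plans 8 years per patient and adds: "At the time of the final analysis, 3076 patients were enrolled in the study". SAP 2.3 says "the study is ending on 28 August 2020, and a single final study report will be submitted in 2021".

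**The concern.** The patient number and the follow-up were both reduced in Protocol Amendment 5, while the person-time and the three rate ratios stayed as they were. A total of 25,000 over 3045 patients needs 25,000 / 3045 = 8.21 years from every patient, more than the 8 years planned and before any drop-out.

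This is a post-approval safety commitment with malignancy as its primary outcome, and two of the three powered outcomes are malignancies. If few events occur, readers will use the stated power to judge what increase in risk the registry could have seen. The SAP also returns to these ideas. In 5.1, "A summary of expected and actual patient retention by enrollment cohort and actual treatment at Baseline will include total patient-years", and 25,000 is the only expected total that the documents give. Sections 4.5 and 8.1.5 make further stratification by duration of prevalent use depend on sufficient power.

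**Working it through.** **Inputs.** N = 3045 (1371 Cimzia, 1674 comparison), 8 years and 8% per year, from Protocol 6.3; N = 3076 at final analysis, from SAP 2.4; study end 28 August 2020, from SAP 2.3. The superseded design of 4000 patients and 10 years, in the Amendment 5 log, is used only to look for the figure's origin.

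**Formula.** Patient-years = N × expected years retained per patient. With continuous drop-out over 8 years this is (1 − 0.92^8) / (−ln 0.92) = 5.838 years. The documents do not name a convention, so six were tried.

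| Drop-out convention | Years per patient (8 y) | 3045 patients, 8 y | 3076 patients, 8 y | 4000 patients, 10 y |
|---|---|---|---|---|
| Continuous | 5.838 | 17,777 | 17,958 | 27,134 |
| 8% of those remaining, at year end | 6.085 | 18,528 | 18,717 | 28,281 |
| 8% of those remaining, at year start | 5.598 | 17,046 | 17,219 | 26,018 |
| 8% of original N, at year end | 5.760 | 17,539 | 17,718 | 25,600 |
| 8% of original N, mid-year | 5.440 | 16,565 | 16,733 | 24,000 |
| 8% of original N, at year start | 5.120 | 15,590 | 15,749 | 22,400 |
| No drop-out | 8.000 | 24,360 | 24,608 | 40,000 |

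**Reproducing 25,000.** No current input set reaches it. The superseded 4000 patients come within 3% in two ways: 25,600 (10 years, linear, year end) and 24,339 (8 years, 8% of those remaining, year end). The figure is compatible with the earlier design, but its exact derivation cannot be identified.

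**By cohort (continuous).** Cimzia: 1371 × 5.838 = 8,004. Comparison: 1674 × 5.838 = 9,773. Without drop-out the Cimzia cohort gives 1371 × 8 = 10,968, below the stated 12,500.

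**The SAP's 10 years.** Taken literally, 3045 patients over 10 years give at most 21,529 with 8% drop-out. SAP 3.1 in any case limits the tables to 8 years.

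**The study end.** Patients enrolled after August 2012 cannot complete 8 years by 28 August 2020. No accrual curve is given. Assuming uniform accrual from January 2009 to March 2017, 3045 patients give about 15,500 patient-years; assuming uniform accrual over the first 5 years, about 17,500.

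**Size of the shortfall.** 1 − 17,777 / 25,000 = 29% (26% to 38% across conventions). Put the other way, 25,000 / 17,777 = 1.41, an overstatement of 41%.

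**Power, as an illustration only.** Assume power was exactly 80% at P0 = P1 = 12,500, and solve for the control rate r0 in

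power = Φ( ln RR / √[1/(r0·P0) + 1/(RR·r0·P1)] − 1.96 ).

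For RR 1.5, r0 = 0.64 per 100 patient-years. At P1 = 8,004 and P0 = 9,773 the expected events are about 76.4 (Cimzia) and 62.2 (comparator). The standard error is √(1/62.2 + 1/76.4) = 0.171, and power is Φ(0.405/0.171 − 1.96) = 0.66.

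| Outcome | RR | Back-solved r0 per 100 p-y | Power at 8,004 / 9,773 | RR detectable at 80% | r0 that would keep 80% |
|---|---|---|---|---|---|
| Serious infections | 1.5 | 0.64 | 66% | 1.60 | 0.89 (+39%) |
| Lymphoma | 3.3 | 0.057 | 68% | 3.9 | 0.077 (+34%) |
| Solid malignancies | 1.56 | 0.52 | 66% | 1.68 | 0.72 (+39%) |

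**The analysed split is not the enrolment split.** Under SAP 3.2.1.1, "Any patient exposed to Cimzia during the study will only contribute person-time to the Cimzia cohort from that point onward". If the Cimzia share of 17,777 lies anywhere from 40% to 60% (assumed), power in the same illustration is 62–66% for serious infections, 60–69% for lymphoma and 62–66% for solid malignancies. The serious-infection range is subject also to the SAP's acute-event rule, which separates gap and overlap time.

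**The case against.** The strongest reply is that nothing in the analysis depends on 25,000. SAP 2.1.1 declares all analyses descriptive, enrolment is closed, and the SAP amendment dated 1 September 2020 follows the study end, so observed patient-years and confidence intervals will show the precision directly. That stands, and it limits the harm to a misleading benchmark. It does not make the statement correct: both documents still assert the power in the present tense, and Protocol 6.3 attaches it to 8 years.

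Second, the text says at least 80% and gives no control rates, so a loss of 80% power is not shown for any outcome. This also stands. If the design had about 90% to 91% power at 12,500 per arm, 80% would survive at 8,004 / 9,773. Neither document claims that, so the right word is unsupported.

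Third, the links to SAP 5.1, 4.5 and 8.1.5 are inferred, since none of them cites 25,000 or SAP 2.4. That is fair. They show where the figure could be used, not that it is.

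Fourth, the opening paragraph of SAP 2.4 can be read as the original design basis, with the amended facts following. But it carries no such label, and it contradicts Protocol 6.3 on the follow-up for the same three rate ratios.

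**Conclusion.** The concern holds. On the stated 3045 patients, 8 years and 8% annual drop-out, the expected person-time is about 17,800 patient-years (15,600 to 18,500), or about 18,000 with 3076 patients, against the stated 25,000. The failure does not depend on the drop-out convention, because even complete retention falls short in total and clearly so in the Cimzia cohort. For the SAP, about 17,800 is likely to be generous, given the August 2020 end.

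The claim of at least 80% power is therefore unsupported in both documents. The 66% to 68% figures rest on the assumption that power was exactly 80% at 12,500 per arm, and they illustrate the scale only. The 8-year and 10-year statements for the same rate ratios contradict each other. The consequence is a wrong statement of the registry's size and precision. No test, estimate or decision rule is affected.

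**What to change.** - **Protocol 6.3:** restate the expected patient-years by cohort for 3045 patients, 8 years and 8% annual drop-out, and name the drop-out convention.
- **SAP 2.4:** restate the patient-years for the enrolled number with the 28 August 2020 end or, better, use observed patient-years under the malignancy and acute-event exposure rules. If the 25,000 is kept, label it as the original design assumption.
- **Both:** state the control rates, and recompute power or the minimum detectable rate ratio for each of the three outcomes.
- **SAP 2.4:** remove the 10-year wording so that it agrees with the 8 years planned. Delete the duplicated enrolment paragraph at the same time.
- **SAP 5.1:** say which expected total is used in the retention table.

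The cost is a recalculation and revised wording in two sample-size sections, plus one clarifying line in SAP 5.1. No patients or data are added. The price is a less favourable stated figure.
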